2.1 Study design with the rationale for its' choice

This is a multi-centre, observational, ambispective study, which will retrospectively and prospectively collect clinical and socio-demographic data from medical records of patients with HTN and dyslipidemia initiated with SPC of amlodipine/atorvastatin/perindopril in real clinical settings.

For parameters of the primary end-point such as BP and LDL-C **a Baseline data** is defined as values of these parameters present in medical records at the nearest date preceding the start of SPC amlodipine/atorvastatin/perindopril. Therefore BP and LDL-C **Baseline data** will be collected retrospectively from medical records of patients with HTN and dyslipidemia. To be included in the study for further prospective observation a patient should have been administered with SPC of amlodipine/atorvastatin/perindopril within one month before the Index Date. The Index date is a date when a decision to include a patient in the study for further 12 week prospective observation made by a treating physician after evaluation of recorded data to confirm patient's eligibility for the study. Once an investigator makes sure that a patient meets all inclusion/non-inclusion criteria the investigator will discuss with the patient during his/her next visit and obtain the signed patient's informed consent to participate in the study (V0).

SPC of amlodipine/atorvastatin/perindopril will be administered to the patients in accordance to the instruction for medical use approved in the Russian Federation. Decision on this medicinal product administration will not be dependent on the decision to include a patient into the observational study and according to the study protocol, such decision should precede treating investigator's intention to include a patient in the study.

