1.3 Study variables

Primary variables:

- Mean change from baseline (BL) in SBP and DBP assessed at week 12 of the observational period.
- Mean change from BL in LDL-C assessed at week 12 of the observational period.

Secondary variables:

- Mean change from BL in SBP and DBP assessed at week 4 of the observation period.
- Proportion of the patients aged 18-64 years who reached SBP <140 mm Hg and DBP <90 mm Hg at week 4 of the observation period.
- Proportion of patients aged 18-64 years who reached target SBP <130 and \geq 120-mm Hg and DBP between 70 and79 mm Hg at week 12 of the observation period.
- Proportion of patients older than 65 years who reached SBP < 140 mm Hg and DBP < 90 mm Hg at week 4 of the observation period.
- Proportion of patients older than 65 years who reached SBP \leq 139 and \geq 130 mm Hg and DBP between 70 and79 mm Hg at week 12 of the observation period.
- Proportion of patients at very high CV risk who reached LDL-C decrease \geq 50% from BL and reached target < 1,4 mmol/l (55 mg/dl) or at week 12 of the observation period.
- Proportion of patients at high CV risk who reached LDL-C decrease \geq 50% from BL and reached target LDL-C < 1,8 mmol/l (70 mg/dl) at week 12 of the observation period.
- Proportion of patients at moderate CV risk who reached target LDL-C < 2,6 mmol/l (100 mg/dl) at week 12 of the observation period.
- Proportion of patients at different CV risk who reached both BP and LDC-C targets
- Proportion of patients aged 18-64 years at very high CV risk who reached SBP <130 and \geq 120 mm Hg and DBP between 70 and79 mm Hg at week 12 of the observation period in the subgroups of the patients receiving SPC of amlodipine/atorvastatin/perindopril in the following dosages 5;20;5 mg and 5;20;10 mg and 5;10;5 mg respectively;
- Proportion of patients older than 65 years at very high CV risk who reached SBP \leq 139 and \geq 130 mm Hg and DBP between 70 and79 mm Hg at week 12 of the observation period in the subgroups of patients receiving SPC of amlodipine/atorvastatin/perindopril in the following dosages 5;20;5 mg and 5;20;10 mg and 5;10;5 mg respectively
- Proportion of patients at very high CV risk who reached LDL_C decrease \geq 50% from BL and reached target <1,4 mmol/l (55 mg/dl) or at week 12 of the observation period in the subgroups of the patients receiving SPC of amlodipine/atorvastatin/perindopril in the following dosages 5;20;5 mg and 5;20;10 mg and 5;10;5 mg respectively;

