2.4 Selection of patients

2.4.1 Inclusion criteria

1. Obtained signed informed consent from the patient
2. Patients of 18 years and older and younger than 80 years.
3. Start of the treatment with SPC of amlodipine/atorvastatin/perindopril within 1 month from the Index date in accordance with the indication in Russian SmPC.
4. Presence of the parameters of interest* in the medical records dated with the nearest to the start of SPC amlodipine/atorvastatin/perindopril treatment date.

* Parameters of interest include measured at rest office BP and LDL-C.

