2.7.2 Study schedule and plan

According to the design of this multicentre, non-intervention, observational study in patients with HTN and dyslipidemia treated with SPC of amlodipine/atorvastatin/perindopril, three visits will be appointed to include patients and to gather parameters of interest to describe treatment effectiveness and safety of the FDC.

Following visits will be appointed:

1. Inclusion Visit 0 (V0) – month 0;
2. Follow up Visit 1 (V1) – 4 weeks after V0;
3. Final Visit 2 (V2): 12 weeks after V0;

Table 1 – Planned study visits

Procedure	Retrospective evaluation of patient's eligibility	Inclusion Visit 0 Month 0	Follow up visit V1 (4 weeks ± 2 weeks)	Final visit V2 (12 weeks ± 2 weeks)
Written informed consent		×		
Assessment in accordance with inclusion/ non-inclusion criteria	×	×		
Demographics		×		
Risk factors and life style		×		
Cardio-vascular disease history		×		
Physical examination with the measurement of BP at rest		×	×	×

LDL-C		×		×
Current treatment with concomitant cardiovascular medications/ changes and reasons		×	×	×
Current treatment with other concomitant medications		×	×	×
Medication adherence scale		×	×	×
Quality of life evaluation (SF-36)		×	×	×
Treatment with the SPC amlodipine/atorvastatin/perindopril status		×	×	×
SPC amlodipine/atorvastatin/perindopril dosage correction (if occurred)		×	×	×
Adverse events/drug reactions/special situations reporting		×	×	×

2.7.4. Data collection:

Data evaluation during the screening period:

HCPs participating in the study will conduct a retrospective analysis of patient's records for the purpose of evaluating patient's eligibility to be enrolled in the study. Patients with HTN and dyslipidemia who had been initiated with SPC amlodipine/atorvastatin/perindopril within one month before the Index Date and who meet other inclusion / non inclusion criteria will be included in the study if they sign a consent form at the inclusion visit.

Data collection at the inclusion visit (V0):

- Obtaining patient informed consent;
- Checking for inclusion/non-inclusion criteria;
- Demographics, CVD history, cardiovascular risk factors (appendix 8)
- Physical examination and vital signs (BP);
- Current status of taking SPC amlodipine/atorvastatin/perindopril and dose regimen;
- SBP, DBP and LDL-C according to the medical records dated with the nearest to the start of treatment with SPC amlodipine/atorvastatin/perindopril;

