- Concomitant current use of any other cardiovascular medications (i.e. antihypertensive, anti-ischaemic, anti-platelet, anticoagulant medications) and any other concomitant medications
- Baseline assessment of adherence to SPC amlodipine/atorvastatin/perindopril done by medication adherence scale;

- Quality of life assessment (questionnaire SF-36)
- Adverse events/drug reactions/special situations

Data collection at the Follow up Visit (V1):

- Physical examination and vital signs (BP);
- Current status of taking SPC amlodipine/atorvastatin/perindopril and dose regimen correction if needed;
- Assessment of adherence to SPC amlodipine/atorvastatin/perindopril done by medication adherence scale;
- Quality of life assessment (questionnaire SF-36)
- Concomitant current use of other cardiovascular medications and any other medications
- Adverse events/drug reactions/special situations

Data collection at the Final Visit (V2):

- Physical examination and vital signs (BP);
- Current status of taking SPC amlodipine/atorvastatin/perindopril and a dose regimen correction if needed;
- LDL-C assessment;
- Assessment of adherence to SPC amlodipine/atorvastatin/perindopril done by medication adherence scale;
- Quality of life assessment (questionnaire SF-36)
- Concomitant current use of other cardiovascular medications and any other medications
- Adverse events/drug reactions/special situations

[figure not shown]

Figure 1. The scheme of TARGET study

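### Inclusion criterion 4 and the V0 list loosen section 2.1's pre-treatment baseline to the value nearest SPC start, so an on-treatment BP or LDL-C could be entered as baseline

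*Combined protocol and SAP*

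**What the plan says.** Section 2.1 defines baseline for the primary-endpoint parameters, BP and LDL-C, as "values of these parameters present in medical records at the nearest date preceding the start of SPC amlodipine/atorvastatin/perindopril", and says that these data are collected retrospectively from the records.

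Inclusion criterion 4 (section 2.4.1) requires that BP and LDL-C be present "in the medical records dated with the nearest to the start of SPC amlodipine/atorvastatin/perindopril treatment date". The V0 list in section 2.7.4 has the site collect "SBP, DBP and LDL-C according to the medical records dated with the nearest to the start of treatment" with SPC. Neither passage says that the value must come before the start.

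Section 2.1 also fixes the order of events: SPC is started within one month before the Index Date, and consent (V0) is taken at the patient's next visit.

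The baseline feeds the primary variables in section 1.3, for example "Mean change from BL in LDL-C assessed at week 12 of the observational period". It also feeds the secondary variables that require an LDL-C fall of at least 50%, such as the one beginning "Proportion of patients at very high CV risk who reached LDL-C decrease".

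**The concern.** The section that defines baseline gives a direction in time. The two passages that a site applies when it screens a patient and fills in V0 data do not. Under their wording, a value dated shortly after SPC start is acceptable if it lies closer to the start than the last value before it.

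The study has one arm and its primary variables are changes from this baseline, so no comparator would absorb an error in it. An on-treatment value entered as baseline already contains part of the response, and the recorded change would probably be too small. The 50% LDL-C criteria would be harder to meet for the same reason.

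**Working it through.** **1. The plan's own figure.** The LDL-C sample size in section 2.2 rests on this baseline. Inputs: baseline 3.09 and week-12 mean 2.65 mmol/l, SD 1.01, margin -0.22, Z values 2.326 and 1.282.

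n = 1.01² × (2.326 + 1.282)² / (2.65 - 3.09 + 0.22)² = 1.0201 × 13.018 / 0.0484 = 274.4. The plan states 274. The point below does not alter this calculation.

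**2. The passages side by side.**

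| Place | Source | Date rule | Must precede SPC start? |
|---|---|---|---|
| Section 2.1 | Records | Nearest date before the start | Yes |
| Section 2.4.1, criterion 4 | Records | Nearest to the start | Not stated |
| Section 2.7.4, V0 list | Records | Nearest to the start | Not stated |

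**3. Do the rules pick different values?** Suppose the last value before SPC start is *a* days before it and the first value after it is *b* days after. Section 2.1 always takes the earlier value. The other two passages, read literally, take the later one whenever *b* < *a*. A patient with only a post-start value meets criterion 4 as worded but has no baseline under section 2.1.

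**4. Can post-start values be in the records?** One month is 30.44/7 = 4.35 weeks. By V0 a patient has been on SPC for 0 to 4.35 weeks, plus the gap between Index Date and V0, which the plan does not give. Such values can therefore exist.

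**5. Size.** Let *p* be the share of patients with an on-treatment baseline, *g* the part of the effect already present in it, and *D* the assumed mean change. If affected patients respond like the rest, the shortfall in the mean change is *p* × *g* × *D*. From section 2.2:

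- SBP: *D* = 158.5 - 132.2 = 26.3 mmHg
- DBP: *D* = 91.7 - 80.1 = 11.6 mmHg
- LDL-C: *D* = 3.09 - 2.65 = 0.44 mmol/l

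The documents give neither *p* nor *g*. Taking each as 0 to 1, the shortfall runs from 0 to *D*, which is a bound and not an estimate. Each 0.10 of *p* × *g* would cost 2.63 mmHg, 1.16 mmHg and 0.044 mmol/l respectively.

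**6. Effect on the 50% criterion.** As an illustration, take one patient at the plan's assumed LDL-C means. From 3.09, a 50% fall requires 3.09 × 0.5 = 1.545 mmol/l or less. If 2.65 were entered as baseline, it would require 2.65 × 0.5 = 1.325 or less. A week-12 value above 1.325 and below the very-high-risk target of 1.4 would meet both conditions against the true baseline and fail the 50% condition against the on-treatment one.

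**The case against.** The strongest reply is that the plan has only one definition of baseline, the one in section 2.1, and it is explicit. Section 2.7.1 gives every doctor a copy of the protocol. Criterion 4 can be read as a check that a record exists and the V0 list as a statement of source, both shorthand for section 2.1. The case report form and Figure 1 are not available here and may enforce the order. All of this lowers the chance of error. It does not remove the conflict: no passage says which wording prevails, and 80 doctors have to apply it.

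Several stronger readings are tempting, and the documents do not support them:

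- **Table 1 schedules an on-treatment LDL-C as baseline.** A reader might infer this because LDL-C is marked at V0 and the first column is blank. That column is headed "Retrospective evaluation of patient's eligibility" and covers only the eligibility check. Section 2.7.4 takes the V0 LDL-C only from records and lists a new LDL-C assessment only at V2. The mark fits transcription of a record value, though the table does not say so.
- **Two BP values at V0 leave baseline open.** The V0 list gives the examination BP and the record BP as separate items, and section 2.1 says that baseline comes from records.
- **The word baseline is used loosely for adherence.** The V0 list does include "Baseline assessment of adherence to SPC amlodipine/atorvastatin/perindopril done by medication adherence scale", an on-treatment measure. But section 1.3 keeps the reference points apart: BP and LDL-C changes are from BL, while SF-36 and adherence are compared with V0.
- **The direction of bias is certain.** Non-inclusion criterion 3 bars concomitant use of similar drugs, not earlier use. In a patient switched from such drugs, an early on-SPC value may differ little from the one before.

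**Conclusion.** The concern holds as a conflict between stated rules. Section 2.1 requires a baseline from before SPC start; criterion 4 and the V0 list do not. The likely consequence is some understatement of the primary changes in SBP, DBP and LDL-C and of the 50% LDL-C attainment rates. This rests on two assumptions: that some sites follow the looser wording literally, and that the early on-treatment values they enter are lower than the pre-treatment ones. The documents do not allow the size to be estimated.

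A reader might infer that the study loses power. With 274 completers and the plan's one-sided 1% level, power for LDL-C is Φ((0.44(1 - L) - 0.22) × √274 / 1.01 - 2.326), where L is the share of the mean change lost. That gives 90% at L = 0, 71% at L = 10% and 44% at L = 20%. These values of L are pure assumptions, so this is no finding about power.

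A reader might also see a conflict between V2 at 12 weeks after V0 and the three months of therapy in section 2.2. Nominal time on SPC at V2 is 12 to 12 + 4.35 = 16.3 weeks, before any gap between Index Date and V0. Three months (3 × 4.35 = 13.0 weeks) lies inside that range, so no change is needed on that account.

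**What to change.** - Put section 2.1's rule, the last recorded value before SPC start, into inclusion criterion 4 and the V0 list in section 2.7.4.
- State whether a same-day value taken before the first dose counts. Read literally, section 2.1 may exclude it, although a BP taken at the prescribing visit is a natural baseline.
- Footnote Table 1 to say that the V0 LDL-C is the pre-SPC value from the records.
- Record the SPC start date and the dates of the baseline BP and LDL-C values. Identify any baseline dated on or after SPC start, subject to the same-day rule, and give the count in the report.

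The cost is a few wording edits and up to three date fields. It may be fewer, since criterion 3 and the duration-of-therapy predictor in section 1.3 already need the timing of SPC start. The sample size does not change. A patient with no value before SPC start would no longer meet criterion 4, but that patient has no baseline under section 2.1 in any case. The section 2.2 hypotheses can stay as they are, and no added analysis of time on SPC is needed, since it would not repair a misdated baseline.

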1.2 Objectives

Primary objective is to describe antihypertensive and hypolipidaemic effectiveness of a triple single-pill combination of amlodipine, atorvastatin and perindopril at 12 weeks in patients with arterial hypertension (HTN) and dyslipidemia in the daily clinical practice.

Secondary objectives

- To determine the proportion of patients who reached systolic (SBP) and diastolic blood pressure (DBP) target goals at weeks 4 and 12 of the observation period respectively.
- To determine the proportion of patients who reached LDL-C target goals at week 12 of the observation period.
- To evaluate the quality of life of patients at visit 1 (V1) and visit 2 (V2) as compared to visit 0 (V0) respectively.
- To evaluate the adherence to treatment with the fixed dose combination (FDC) of amlodipine/atorvastatin/perindopril in patients included into the study at V1 and V2 as compared to V0.
- To evaluate predictors of reaching BP and LDL-C target goals in the study population.

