2.4.2 Non-inclusion criteria

1. Subjects who are unwilling or unable to provide a signed informed consent form;
2. Any contraindication to the treatment with the SPC of amlodipine/atorvastatin/perindopril according to its' approved instruction for medical use in the Russian Federation;
3. Concomitant use of any other ACE inhibitors, CCBs, ARBs and statins.
4. Supposed low treatment adherence to the assigned SPC and the risk for poor collaboration between the patient and the investigator during the study;
5. Any severe, decompensated or unstable somatic diseases or states that according to investigator discretion are life-threatening or worsen the prognosis for the patient: myocardial infarction in the past 3 months, unstable angina, current decompensation of diabetes mellitus, autoimmune or oncological diseases, severe cardiac arrhythmia,

gastrointestinal disorders affecting absorption, severe hepatic diseases, pancreatic diseases, severe allergic reactions, connective tissue diseases etc;

6. Secondary arterial hypertension;
7. Alcohol or any drug abuse;
8. Surgical intervention on heart or coronary vessels (i.e., heart valve(s) replacement, stent implantation or CABG), or any non-cardiological serious surgical intervention that are planned within next 3 months and may require withdrawal or changes in current therapy;
9. Glomerular filtration rate less than 60 ml/min/1,72m²;
10. Participating in any other clinical trial currently or during 30 days period before informed consent was signed.

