2.7 Documentation of the non-interventional clinical study

2.7.1. Documentation folder

Each doctor will be provided with a documentation folder containing a complete set of documents for 5-6 patients + 2 extra sets in case of lost or damage of study documents including:

- One protocol of the observation plan;
- Documents for 5-6 patients (12 *Patient Informed Consent Forms*, with 5-6 *Adverse event/adverse drug reaction/special situation reporting forms*).
- 2 extra sets in case of lost or damage of study documents (*Patient Informed Consent Form*,; *Adverse event/adverse drug reaction/special situation reporting forms*)

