3.2 Responsibilities

3.2.1 Events to be reported

All available information about the following reported events occurring during the study will be recorded. All reported AEs/ADRs will be described in the statistical analysis report.

- All serious adverse drug reactions related to the use of amlodipine/atorvastatin/perindopril FDC;
- All non-serious adverse drug reactions related to the use of SPC amlodipine/atorvastatin/perindopril);
- All reports about special situations (see 3.1.1);

- All adverse events

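### Baseline precedes treatment, but patients are chosen after it has begun, with no consecutive-invitation rule and no log of starters, so the primary change can overstate the effect in daily practice

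*Combined protocol and SAP*

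**What the plan says.** Section 2.1 defines baseline blood pressure and LDL-C as the recorded values closest to, and before, the start of the SPC. To qualify, a patient "should have been administered with SPC of amlodipine/atorvastatin/perindopril within one month before the Index Date". The Index date is that of the "decision to include a patient in the study for further 12 week prospective observation made by a treating physician after evaluation of recorded data"; the sentence goes on to give confirmation of eligibility as the purpose of that evaluation. Consent follows at the patient's next visit, which is V0, and no limit is set on the gap. Under section 2.7.2, week 12 is counted from V0.

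Inclusion criterion 3 (section 2.4.1) asks for "Start of the treatment with SPC of amlodipine/atorvastatin/perindopril within 1 month from the Index date". Section 2.4.2 bars patients who also use another ACE inhibitor, calcium channel blocker, ARB or statin (criterion 3), and those with "Supposed low treatment adherence to the assigned SPC and the risk for poor collaboration between the patient and the investigator during the study" (criterion 4). Table 1 has the criteria checked at the record review and again at V0, where blood pressure is also measured.

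Section 2.3 plans 80 doctors, and section 2.7.1 gives each "a complete set of documents for 5-6 patients + 2 extra sets in case of lost or damage of study documents". The primary objective (section 1.2) is to describe effectiveness "at 12 weeks in patients with arterial hypertension (HTN) and dyslipidemia in the daily clinical practice". On safety, section 3.2.1 says: "All available information about the following reported events occurring during the study will be recorded".

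**The concern.** The first weeks on treatment count towards the primary change, but only for patients who were selected after those weeks had begun and who came back. A doctor may by then know how the patient tolerated the SPC and, if blood pressure was taken in the meantime, how it responded. Nothing obliges the doctor to invite eligible patients in order, and nothing records those who were not invited.

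Two non-inclusion criteria can act on post-start events. A patient moved to another drug of a listed class becomes ineligible, and so does one whom the doctor now expects to adhere poorly, although adherence is itself a secondary outcome.

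At stake is whom the result describes. If the missing patients did worse than those included, the mean blood pressure change, the proportions at target, the adherence categories and the tolerability profile are all too favourable as a picture of daily practice. The 30% drop-out allowance in section 2.2 concerns losses during the study and does not cover losses before V0. Section 4.2 cannot correct for them either, because no data on them are collected.

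**Working it through.** **The plan's own figures.** Section 2.2 assumes systolic pressure of 158.5 mmHg at baseline and 132.2 mmHg at three months, a change of 132.2 - 158.5 = -26.3 mmHg, with SD 16.7 and margin -13.15. Its formula gives 16.7² × (2.326 + 1.282)² / (-26.3 + 13.15)² = 21.0, matching the stated 21. For LDL-C, 1.01² × 3.608² / (-0.44 + 0.22)² = 274.4 (stated 274). With 30% drop-out, 274 / 0.7 = 391.4, so 392; the plan takes 400. Then 400 / 80 = 5 patients per doctor, which fits the folder size. The sample size is not in dispute.

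**Sequence of events.**
1. Last blood pressure and LDL-C before the SPC: the baseline.
2. SPC start.
3. Up to one month later, the Index date: the doctor decides on inclusion.
4. Next visit, at an unspecified interval: V0, consent, criteria checked again.
5. Twelve weeks after V0: the primary assessment.

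Selection at steps 3 and 4 falls between the two measurements whose difference is the primary variable. That is enough for selection related to outcome to enter it. The documents give no rate of early loss and no strength of selection, so the following are illustrations on assumed inputs.

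**Illustration A: loss before V0.** Assume a share s of starters is lost before V0 with no change in pressure, and that the planned -26.3 mmHg holds in those included. The all-starter change is (1 - s) × (-26.3).
- s = 0.05: 0.95 × (-26.3) = -25.0 mmHg
- s = 0.15: 0.85 × (-26.3) = -22.4 mmHg

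**Illustration B: selection on early response.** Assume the worst share q by early systolic response is left out, that early response and week-12 change are jointly normal with correlation r, and that the SD of the change is 16.7 mmHg (the plan's figure, borrowed). The mean fall is inflated by r × 16.7 × φ(z_q) / (1 - q), with φ(z_q) = 0.1755 at q = 0.10 and 0.2800 at q = 0.20.

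| q | r = 0.3 | r = 0.5 |
|---|---|---|
| 0.10 | 0.98 mmHg | 1.63 mmHg |
| 0.20 | 1.75 mmHg | 2.92 mmHg |

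This is 1.0-2.9 mmHg, or about 4% to 11% of 26.3.

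A and B are alternatives. Patients who stop early and those who respond worst are likely to be largely the same people, so the two should not be added.

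**LDL-C.** No on-treatment value is scheduled before V0, and section 2.7.4 takes the V0 entry from the records nearest SPC start. Selection on observed LDL-C response is therefore less plausible. Selection through not returning, stopping or adherence remains possible.

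**The case against.** The record review is described as an eligibility check, and the values it must find are those nearest the start of treatment. No on-treatment blood pressure is required before the Index date, so knowledge of early response is possible but not shown. This stands, and it is why the conclusion speaks of what can happen.

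The prescribing decision must precede any intention to include the patient. That is a sound safeguard against the study driving prescribing, but it does not govern selection after treatment starts.

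The objective does not promise an estimate for everyone who starts the SPC. That also stands. The remedy is therefore partly a matter of saying whom the result covers.

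The illustrations rest on assumed inputs, and zero change in those lost is an extreme case, since they may receive other treatment. Even so, -22.4 mmHg lies well beyond the -13.15 mmHg margin. The exposure is to the described size of effect more than to the planned systolic comparison.

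Four stronger readings are tempting but not supported:
- **Early stoppers are excluded.** Criterion 3 asks only that treatment was started, and V0 records SPC status. Stopping alone does not bar a patient.
- **Each doctor fills a quota.** Section 2.7.1 describes document sets, with spares and 12 consent forms. Five per doctor is an average inferred from 400 and 80; no stopping rule is stated.
- **Adverse events before V0 are lost.** V0 already includes adverse event collection. Only the look-back period is unstated.
- **The effect is certainly overstated.** The documents show a route for bias, but neither its occurrence nor its size.

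**Conclusion.** The concern holds as a risk built into the design. With a pre-treatment baseline, inclusion decided after treatment has begun, entry dependent on returning, and two criteria that can act on post-start events, the plan as written permits selection related to outcome and gives no means of seeing how much occurred. Blood pressure change, target proportions, adherence and tolerability can be overstated as a description of daily practice; LDL-C is less exposed.

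The size is not derivable from the documents. The ranges above depend wholly on assumed loss of 5-15% with no change or, alternatively, on omission of the worst 10-20% at correlation 0.3-0.5. They indicate scale only. This is a cheap improvement to the plan, not a defect that invalidates it.

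**What to change.** In sections 2.1 and 2.7.4, require each doctor to invite all eligible patients started on the SPC from a set date, in order of start date, whatever their early response and whether or not they are still taking it at V0, until the site's planned number is reached.

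Keep a site log of SPC starts in that window, holding anonymous counts only, because sections 2.7.5 and 5 rest participation and data transfer on written consent. Count those included; those not included, by reason (non-inclusion criterion 3, criterion 4, other criteria, not returned, declined); and those who stopped the SPC before V0, where known. Counting under criteria 3 and 4 matters because consecutive invitation of eligible patients does not reach people whom those criteria remove.

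Report the counts beside the primary result and state that the result applies to patients included at V0. State also that adverse event collection at V0 covers the period since SPC start.

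The cost is a short log per doctor, possibly slower enrolment, and perhaps a slightly less favourable estimate. The sample size does not change.
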